3.2.5.1 Management of stomatitis/oral mucositis/mouth ulcers

Stomatitis/oral mucositis/mouth ulcers due to RAD001 should be treated using local supportive care.

When described, the disorder has been identified as inflammation or ulcers in the mouth. If exam reveals mouth ulcers, rather than a more general inflammation of the mouth, please classify the adverse event as „mouth ulcers“. If inflammation is limited to the mouth without ulcers please use the term „stomatitis“ rather than the less specific term „mucositis“.

If the disorder is elsewhere than the mouth please describe the location as well as any specific procedures carried out for exploration (e.g. endoscopy).

Please use the Grading according to the NIH-NCI Common Terminology Criteria for Adverse Events, Version 3.0 (CTCAEv3.0; <http://ctep.cancer.gov/forms/CTCAEv3.pdf>).

- Grade 1: minimal symptoms; normal diet
- Grade 2: symptomatic but can eat and swallow modified diet
- Grade 3: symptomatic and unable to adequately aliment or hydrate orally
- Grade 4: symptoms associated with life-threatening consequences

Recommendations

1. To help avoid these effects patients should brush their teeth with a very soft toothbrush and if gums bleed patients should be instructed to brush their teeth with gauze instead, use an alcohol-free mouthwash up to 3 times a day, eat soft bland foods like puddings milkshakes and cream soups, avoid spicy, crunchy, acidic and very hot foods.
2. For mild toxicity (Grade 1), use conservative measures such as non-alcoholic mouth wash or salt water (0.9%) mouth wash several times a day until resolution.
3. For more severe toxicity (Grade 2 in which case patients have pain but are able to maintain adequate oral alimentation, or Grade 3 in which case patients cannot maintain adequate oral alimentation), the suggested treatments are topical analgesic mouth treatments (i.e., local anesthetics such as benzocaine, butyl aminobenzoate, tetracaine hydrochloride, menthol, or phenol) with or without topical corticosteroids, such as triamcinolone oral paste 0.1% (e.g. Kenalog in Orabase®).

Agents containing hydrogen peroxide, iodine, and thyme derivatives may tend to worsen mouth ulcers. It is preferable to avoid these agents. Antifungal agents must be avoided unless a fungal infection is diagnosed. In particular, systemic imidazole antifungal agents (ketoconazole, fluconazole, itraconazole, etc.) should be avoided in all patients due to their strong inhibition of RAD001 metabolism, therefore leading to higher RAD001 exposures. Therefore, topical antifungal agents are preferred if an infection is diagnosed. Similarly, antiviral agents such as acyclovir should be avoided unless a viral infection is diagnosed.

3.2.5.2 Management of hyperlipidemia and hyperglycemia

Treatment of hyperlipidemia should take into account the pre-treatment status and dietary habits. Blood tests to monitor hyperlipidemia must be taken in the fasting state. Hyperlipidemia and hypertriglyceridemia should be treated according to local best clinical practice. Patients should be monitored clinically and through serum chemistry for the development of rhabdomyolysis and other adverse events as required in the product label/data sheets for HMG-CoA reductase inhibitors.

Hyperglycemia has been reported in clinical trials. Monitoring of fasting serum glucose is recommended prior to the start of everolimus therapy and periodically thereafter. Optimal glycemic control should be achieved before starting trial therapy.

3.2.5.3 Management of Hepatitis B reactivation

If any patients experience reactivation of hepatitis B during treatment, the patient will be removed from study protocol and referred to the appropriate specialist for management of Hepatitis B.

3.2.5.4 Management of non-infectious pneumonitis

Non-infectious pneumonitis is a class effect of rapamycin derivatives. Cases of non-infectious pneumonitis (including interstitial lung disease) have also been described in patients taking everolimus (see [Section 5](#) Adverse drug reactions). Some of these have been severe and on rare occasions, a fatal outcome was observed.

A diagnosis of non-infectious pneumonitis should be considered in patients presenting with non-specific respiratory signs and symptoms such as hypoxia, pleural effusion, cough or dyspnoea, and in whom infectious, neoplastic and other non-medicinal causes have been excluded by means of appropriate investigations. Patients should be advised to report promptly any new or worsening respiratory symptoms.

Patients who develop radiological changes suggestive of non-infectious pneumonitis and have few or no symptoms may continue everolimus therapy without dose alteration. If symptoms are moderate (Grade 2), consideration should be given to interruption of therapy until symptoms improve. The use of corticosteroids may be indicated. Everolimus may be reintroduced at a reduced dose until recovery to Grade 1 or better.

For cases where symptoms of non-infectious pneumonitis are severe (Grade 3), everolimus therapy should be discontinued and the use of corticosteroids may be indicated until clinical symptoms resolve. Therapy with everolimus may be re-initiated at a reduced dose depending on the individual clinical circumstances.

Both asymptomatic radiological changes (grade 1) and symptomatic non-infectious pneumonitis (grade 2 = not interfering with activities of daily living or grade 3 = interfering with activities of daily living and oxygen indicated) have been noted in patients receiving RAD001 therapy. Non-infectious pneumonitis has been associated with RAD001 and other mTOR inhibitors (Atkins 2004). In order to monitor for asymptomatic (grade 1) pulmonary infiltrates, a chest X-ray is required if a CT scan of chest is not used for bi-monthly disease evaluations. Additional chest CT scans may be performed, when clinically necessary. If non-infectious pneumonitis develops, a consultation with a pulmonologist should be considered. If the patient develops grade 3 pneumonitis, treatment with RAD001 should be interrupted and the patient should be treated as medically indicated (short course corticosteroids, oxygen, etc). Management of non-infectious pneumonitis suspected to be associated with RAD001 and dose modifications instructions are provided in Table 3-2

Table 3-2 Management of non-infectious pneumonitis

Worst Grade Pneumonitis	Required Investigations	Management of Pneumonitis	RAD001 Dose Adjustment
Grade 1	CT scans with lung windows and pulmonary function testing including: spirometry, DLCO, and room air O₂ saturation at rest. Repeat chest x-ray/CT scan every 2 Cycles until return to baseline.	No specific therapy is required	Administer 100% of RAD001 dose.
Grade 2	CT scan with lung windows and pulmonary function testing including: spirometry, DLCO, and room air O₂ saturation at rest. Repeat each subsequent Cycle until return to baseline. Consider bronchoscopy *	Symptomatic only. Prescribe corticosteroids if cough is troublesome.	Reduce RAD001 dose until recovery to ≤ Grade 1. RAD001 may also be interrupted if symptoms are troublesome. Patients will be withdrawn from the study if they fail to recover to ≤ Grade 1 within 3 weeks.
Grade 3	CT scan with lung windows and pulmonary function testing including: spirometry, DLCO, and room air O₂ saturation at rest.; Repeat each subsequent Cycle until return to baseline. Bronchoscopy is recommended *	Prescribe corticosteroids if infective origin is ruled out. Taper as medically indicated.	Hold treatment until recovery to ≤ Grade 1. May restart protocol treatment within 2 weeks at a reduced dose (by one level) if evidence of clinical benefit. Patients will be withdrawn from the study if they fail to recover to ≤ Grade 1 within 2 weeks.
Grade 4	CT scan with lung windows and required pulmonary function testing includes: spirometry, DLCO, and room air O₂ saturation at rest. Repeat each subsequent Cycle until return to baseline. Bronchoscopy is recommended *.	Prescribe corticosteroids if infective origin is ruled out. Taper as medically indicated.	Discontinue treatment.

*A bronchoscopy with biopsy and/or bronchoalveolar lavage is recommended.

All interruptions or changes to study drug administration must be recorded.

It will be documented whether or not each patient completed the clinical study. If for any patient either study treatment or observations were discontinued the reason will be recorded. Reasons that a patient may discontinue participation in a clinical study are considered to constitute one of the following:

1. After administration of **24** cycles
2. adverse event(s) including re-activation of Hepatitis B
3. abnormal laboratory value(s)
4. abnormal test procedure result(s)

5. disease progression
6. protocol violation
7. subject withdrew consent
8. lost to follow-up
9. administrative problems
10. Medical or psychiatric illness which in the investigator's judgment renders the patient incapable of further therapy.
11. Death
12. Treatment delay due to toxicity greater than **28** days measured from the start of the preceding cycle.

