6.1 Statistical methods

6.1.1. Stopping Rules

If the discontinuation rate due to toxicity is 20% or greater and the lower bound for the one-tailed 95% confidence interval is $> 10\%$, this strategy would not be considered feasible. At the time we observe any toxicity that requires permanent discontinuation of drug, we will estimate, with confidence intervals, the rate of toxicity. If there is a greater than 20% rate for discontinuation of drug during therapy the study will stop and we will assess the study design. Because the confidence interval may be calculated multiple times, the actual confidence level will be overstated. This increases the likelihood of rejecting the therapy due to toxicity. However, this is felt to be an acceptable risk in order to prevent continuation of a therapy that may have a toxicity rate that precludes its routine use.

If there is any treatment related mortality event, the study accrual will be suspended until all data pertaining to the event is reviewed by the Study Chair and co-investigators.

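### Section 3.2.5.4 and Table 3-2 set different restart conditions and time limits for grade 3 pneumonitis, and different default actions for grade 2, and no text states which governs

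*Combined protocol and SAP*

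**What the plan says.** All references are to the combined protocol and SAP.

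**Grade 3.** Section 3.2.5.4 addresses it three times.
- The severity-by-severity narrative says "everolimus therapy should be discontinued and the use of corticosteroids may be indicated until clinical symptoms resolve". Its next sentence adds "Therapy with everolimus may be re-initiated at a reduced dose depending on the individual clinical circumstances".
- The paragraph leading into Table 3-2 says "If the patient develops grade 3 pneumonitis, treatment with RAD001 should be interrupted and the patient should be treated as medically indicated". It closes with a pointer: "Management of non-infectious pneumonitis suspected to be associated with RAD001 and dose modifications instructions are provided in Table 3-2".
- Table 3-2 holds treatment until Grade 1 or better and states "May restart protocol treatment within 2 weeks at a reduced dose (by one level) if evidence of clinical benefit". A patient not recovered within 2 weeks is withdrawn from the study.

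**Grade 2.** The narrative asks the investigator to consider interrupting until symptoms improve, with reintroduction at a reduced dose. Table 3-2 instead says "Reduce RAD001 dose until recovery to" Grade 1 or better, allows interruption if symptoms are troublesome, and withdraws the patient if recovery takes more than 3 weeks.

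**Table 3-1 (Section 3.2.3).** The grade 2 and grade 3 rows exclude pneumonitis and refer to Table 3-2. The grade 3 row nevertheless ends with a line on corticosteroids for pneumonitis.

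**Stopping rule (Section 6.1.1).** The estimate is triggered as follows: "At the time we observe any toxicity that requires permanent discontinuation of drug, we will estimate, with confidence intervals, the rate of toxicity". The sentence that stops the study refers to a rate above 20% for discontinuation during therapy and does not repeat the word permanent.

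**The concern.** The protocol describes non-infectious pneumonitis as a class effect that has been severe and, rarely, fatal. Section 3.2.5 lists it among the most common grade 3-4 reactions. Two investigators with the same patient could act differently, and each could cite current protocol text. That is a safety and consistency problem, whatever its statistical effect.

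There is also a smaller matter of counting. The safety rule in Section 6.1.1 works on toxicity discontinuations. If one text takes a patient off treatment for good and another lets the patient restart, the count depends on which text was followed. It also depends on whether Section 6.1.1 means permanent discontinuation throughout.

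**Working it through.** The plan states no figure on this point that could be reproduced. The check sets the texts side by side.

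**Step 1. Instructions by grade**

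| Grade | Section 3.2.5.4, severity narrative | Paragraph before Table 3-2 | Table 3-2 |
|---|---|---|---|
| 1 | Continue, dose unchanged | No dose instruction | Full dose |
| 2 | Consider interruption; reintroduce at reduced dose; no limit | No dose instruction | Reduce dose; interruption optional; withdraw if not recovered in 3 weeks |
| 3 | Discontinue; may re-initiate at reduced dose, case by case; no recovery grade, limit or benefit condition | Interrupt; pointer to Table 3-2 | Hold to Grade 1 or better; restart within 2 weeks, one level lower, if benefit is evident; withdraw if not recovered in 2 weeks |
| 4 | Not addressed | Not addressed | Discontinue |

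Grade 1 agrees. Grade 4 has one pneumonitis-specific instruction, and the general grade 4 row of Table 3-1 matches it. The differences lie in grades 2 and 3.

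**Step 2. Test cases for grade 3**

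- *Recovery to Grade 1 on day 20 of the hold.* Table 3-2's limit is 2 × 7 = 14 days. Since 20 > 14, the patient is withdrawn. The narrative sets no limit, so the patient may restart. The general toxicity limit does not settle the matter: 20 < 28 when counted from the interruption (Table 3-1), the intended next dose (Section 3.2.4) or the last dose (Section 3.3.2). The list of discontinuation reasons after Table 3-2 counts 28 days from the start of the preceding cycle, so there the answer depends on when in the cycle the hold began.
- *Recovery on day 10 without evidence of benefit.* Here 10 < 14, so the time limit is met, but Table 3-2's benefit condition for restart is not. The narrative imposes no such condition.

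**Step 3. Test case for grade 2**

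Take moderate symptoms that are not troublesome. The table's default is a lower dose with treatment continuing. The narrative's only suggested action is to consider interruption, and it mentions dose reduction only on reintroduction. The table's limit is 3 × 7 = 21 days, with no counterpart in the narrative.

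**Step 4. Link to Section 6.1.1**

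The first part of the rule needs a discontinuation rate of at least 20% and a one-tailed 95% lower bound above 10%. The interval method is not named, so the exact (Clopper-Pearson) bound is assumed: L(x, n) is the 5th percentile of a Beta(x, n − x + 1) distribution.

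- 8/40 = 20.0%, L = 10.4%: met. 7/40 = 17.5%, L = 8.5%: not met.
- 12/60 = 20.0%, L = 12.0%: met. 11/60 = 18.3%, L = 10.6%: not met, because the rate is below 20%.

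The separate above-20% sentence needs 9/40 (22.5%) or 13/60 (21.7%). One patient classified differently can therefore change the result, but only when the count is already at the boundary.

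To say how likely that is, one would need the rate of pneumonitis cases that the texts classify differently. The documents do not give it. Section 3.2.5 gives only an incidence of at least 2% for grade 3-4 pneumonitis, and a 7% permanent-discontinuation rate for all adverse reactions together. Both come from a renal cell carcinoma trial. Neither is the rate required, so the calculation stops here.

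**The case against.** The other side has a good case on several points.

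- **The three verbs are not three outcomes.** A reader might infer that the narrative ends treatment for good at grade 3. It does not, because its next sentence allows re-initiation. All three texts stop the drug at grade 3 and mention corticosteroids. This objection stands. The conflict lies in the conditions and time limit for restart, not in the verb.
- **The table appears to govern.** Section 3.2.3 sends dose changes to Table 3-1, which sends grade 2 and 3 pneumonitis to Table 3-2, and the lead-in paragraph points there too. This is strong evidence of intent. But no sentence gives the table precedence, and the narrative remains in force under the management heading.
- **Grade 2 is weaker.** Both texts make interruption optional, and a missing limit in one does not strictly contradict a limit in the other. What stands is the different default action and a withdrawal limit that appears in only one place.
- **The line in Table 3-1 is editorial.** It agrees with the corticosteroid advice elsewhere and creates no conflicting dose action.
- **Section 6.1.1 partly answers the counting question.** Its trigger requires permanent discontinuation, so a restarted case would not trigger it. The missing word in the stopping sentence is a separate drafting gap, not caused by the pneumonitis text.

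**Conclusion.** The instructions are inconsistent. The firm part is grade 3: the narrative leaves restart to discretion, while Table 3-2 requires recovery, evidence of benefit and a 2-week limit. The difference in the grade 2 default action is real but smaller. Grades 1 and 4 are not in conflict.

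Two stronger inferences should be resisted. First, it is not true that every case held under one text is permanently discontinued under another. Only cases such as those in Step 2 diverge. Second, a reader might raise the 7% discontinuation rate to some higher value and read off a change in the chance of stopping the study. That would not measure this defect. The 7% covers all adverse reactions in a different disease, and nothing in the documents says how many patients would be classified differently. The size of the effect on the stopping rule is therefore unknown.

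The sample size and primary test do not depend on this point. The case for action rests on clear instructions for a potentially fatal toxicity. It assumes only that the narrative remains operative text, as it does in the document.

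**What to change.** - Reconcile the two narrative passages of Section 3.2.5.4 with Table 3-2, so that each grade has one instruction, one set of restart conditions and one time limit. State how that limit relates to the general 28-day limit. Which clinical rule is right is for the investigators and the sponsor to decide, and no preference is expressed here.
- Either move the leftover pneumonitis line in the grade 3 row of Table 3-1 to the reconciled text or delete it.
- State explicitly that the reconciled text governs pneumonitis dosing.
- In Section 6.1.1, use one defined term throughout, and say whether a case that is stopped and later restarted counts towards the discontinuation rate.

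The cost is a wording amendment, with the review that Section 4 requires. No change to sample size, visits or data collection is needed.

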3.3 Treatments

3.3.1 RAD001 Administration

The study drug RAD001 will be self-administered (by the patients themselves). The investigator will instruct the patient to take the study drug exactly as specified in the protocol. RAD001 will be administered orally as once daily dose of **10 mg (two 5 mg tablets)** continuously from study day 1 until progression of disease or unacceptable toxicity. Patients will be instructed to take RAD001 in the morning, at the same time each day.

RAD001 may be taken with or without food.

If vomiting occurs, no attempt should be made to replace the vomited dose.

All dosages prescribed and dispensed to the patient and all dose changes during the study must be recorded.

Medication labels will comply with US legal requirements and be printed in English. They will supply no information about the patient. The storage conditions for study drug will be described on the medication label.

RAD001 will be provided by Novartis. RAD001 is formulated as tablets for oral administration of 5 mg and 10mg strength. Tablets are blister-packed under aluminum foil in units of 10 tablets (16 units per box), which should be opened only at the time of administration as drug is both hygroscopic and light-sensitive.

3.3.2 Duration of Therapy

In the first year of therapy, patients will receive therapy continuously for approximately 2 four week cycles. At the end of every 2 cycles during the first year, patients will receive an MRI and return to clinic for clinical evaluation. The frequency of MRI's is based on clinical practice at the Neuro-oncology department at UCSF for patients on active therapy. Upon re-evaluation, patients who have not experienced excess toxicity or disease progression will continue on protocol therapy.

In the second year of therapy, patients will receive therapy continuously for approximately 3 four week cycles. At the end of every 3 cycles during the second year, patients will receive an MRI and return to clinic for clinical evaluation. Upon re-evaluation, patients who have not experienced excess toxicity or disease progression will continue on protocol therapy.

After administration of RAD001 for 2 years, patients will receive an MRI and return to clinic for clinical evaluation. At that time, they will be offered the opportunity to continue treatment if they have not experienced excess toxicity or disease progression. Patients will continue to be followed at three month intervals if after two years they continue to take RAD001.

The study will be terminated for the patient if treatment is delayed due to toxicity greater than 28 days measured from the last dose of RAD001.

3.3.3 Concomitant therapy

All concomitant medications administered within 14 days of enrollment through treatment termination should be reported to the investigator and recorded in the Case Report Form (CRF). In particular, corticosteroid dosing will be recorded as use of corticosteroids may affect the appearance of T2 changes on MRI imaging. In addition, the definition of response is based on corticosteroid use (see section 3.42).

Patients will be instructed not to take any additional medications (including over-the-counter products) during the course of the study without prior consultation with the investigator. At each visit, the investigator will ask the patient about any new medications he/she is or has taken after the start of the study drug.

All Concomitant medications/Significant non-drug therapies taken \leq 30 days prior to start and after start of study drug, including physical therapy and blood transfusions, should be recorded.

The following restrictions apply during the entire duration of the study:

- No other investigational therapy should be given to patients.
- No anticancer agents other than the study medication should be given to patients. If such agents are required for a patient then the patient must first be withdrawn from the study.
- Oral contraceptives in preclinical and clinical data have shown everolimus to have CYP3A4 inhibitory activity rather than induction activity, induction of metabolism of contraceptive hormones by everolimus is unlikely. Consequently, administration of everolimus should not reduce the efficacy of oral contraceptives.

Inhibitors of CYP3A4 and/or PgP

- Co-administration with strong inhibitors of CYP3A4 (e.g., ketoconazole, itraconazole, ritonavir) or P-glycoprotein (PgP) should be avoided

- Seville orange, star fruit, grapefruit and their juices affect P450 and PgP activity. These juices are potent CYP3A4-inhibitors. Concomitant use should be avoided
- Co-administration with moderate CYP3A4 inhibitors (e.g., erythromycin, fluconazole) or PgP inhibitors should be used with caution. If patient requires co-administration of moderate CYP3A4 inhibitors or PgP inhibitors, reduce the dose of RAD001 to 2.5 mg daily. Additional dose reductions to every other day may be required to manage toxicities. If the inhibitor is discontinued the RAD001 dose should be returned to the dose used prior to initiation of the moderate CYP3A4/PgP inhibitor after a washout period of 2 to 3 days.

Inducers of CYP3A4 and/or PgP

Avoid the use of strong CYP3A4 inducers. If patient requires co-administration of strong CYP3A4 inducers (i.e., phenytoin, carbamazepine, rifampin, rifabutin, Phenobarbital, St. John's wort), an increase in the dose of everolimus from 10mg daily to 20mg daily, using 5mg increments. Enzyme induction usually occurs within 7-10 days, therefore everolimus dose should be increased by one increment 7 days after the start of the inducer therapy. If no safety concerns are seen within the next 7 days, the dose can be increased again one additional increment up to a maximum of twice the daily dose used prior to initiation of the strong CYP3A4 inducer. This dose adjustment of RAD001 is intended to achieve similar AUC to the range observed without inducers. However, there are no clinical data with this dose adjustment in patients receiving strong CYP3A4 inducers. If the strong inducer is discontinued the RAD001 dose should be returned to the dose used prior to initiation of the strong CYP3A4/PgP inducer.

- No chronic treatment with systemic steroids (at a dose equivalent of greater than 20 mg prednisone per day) or other immunosuppressive agents. Topical or inhaled corticosteroids are allowed.
- The use of live vaccines and close contact with those who have received live vaccines should be avoided during treatment with everolimus. Examples of live vaccines include intranasal influenza, measles, mumps, rubella, oral polio, BCG, yellow fever, varicella and TY21a typhoid vaccines.

Oral anticoagulants such as warfarin are CYP2C9 substrates and, as such, no interaction with RAD001 is expected. However, drug-drug interaction studies between macrolide antibiotics and warfarin have produced mixed outcomes and the disparity in these findings has led to the conclusion that multiple factors may alter the clearance of warfarin. The coadministration of RAD001 and oral anticoagulants is possible but should be subject to verification of coagulation (INR) once steady state is reached (after one week's treatment).

Examples are provided in Table 3-3 (CYP3A4 inhibitors/inducers) and Table 3-6 (Drug interactions mediated by P-glycoprotein). A comprehensive list of cytochrome P450 isoenzymes and CYP3A4 inhibitors, inducers, and substrates can be found at

<http://medicine.iupui.edu/flockhart>. This website is continually revised and should be checked frequently for updates.

Table 3-3 Examples of clinically relevant drug interaction: substrates, inducers and inhibitors of isoenzyme CYP3A.

Substrates (competitive inhibition)	
Antibiotics ¹ : clarithromycin* erythromycin telithromycin* Anti-arrhythmics: quinidine Benzodiazepines: alprazolam diazepam midazolam triazolam Immune Modulators: cyclosporine tacrolimus (FK506) HIV Protease Inhibitors: indinavir* nelfinavir ritonavir* saquinavir* Prokinetic: cisapride Antihistamines: astemizole chlorpheniramine terfenadine	Calcium Channel Blockers: amlodipine diltiazem felodipine lercanidipine nifedipine nisoldipine nitrendipine verapamil HMG CoA Reductase Inhibitors ² : cerivastatin lovastatin simvastatin Miscellaneous: Alfentanil, aprepitant, aripiprazole, buspirone, cafergot, caffeine, cilostazol, cocaine, codeine-N-demethylation, dapsone, dexamethasone, dextromethorphan, docetaxel, domperidone, eplerenone, fentanyl, finasteride, Gleevec/imatinib, haloperidol, irinotecan, LAAM, lidocaine, methadone, nateglinide, ondansetron, pimozide, propranolol, quetiapine, quinine, risperidone, salmeterol, sildenafil, sirolimus, sorafenib, sunitinib tamoxifen, taxol, terfenadine, torisel, trazodone, vincristine, zaleplon, ziprasidone, zolpidem
Inducers	
Barbiturates , Carbamazepine Glucocorticoids modafinil, oxcarbazepine, Phenobarbital Phenytoin*, pioglitazone, Rifabutin*	Rifampin* St John's wort Troglitazone efavirenz, nevirapine
Inhibitors	
Strong Inhibitors: indinavir, nelfinavir, ritonavir, clarithromycin, itraconazole, ketoconazole, nefazodone, saquinavir, telithromycin Posaconazole (Krishna et al, 2009)	
Moderate inhibitors: aprepitant, diltiazem, erythromycin, fluconazole, grapefruit juice, verapamil	
Weak inhibitors: Cimetidine, Seville orange (Malhotra et al, 2001)	
Unclassified as per the Indiana University DDI listing:	

Ciprofloxacin, delavirdine, troleandomycin, mibefradil, amiodarone, chloramphenicol, diethyldithiocarbamate, fluvoxamine, starfruit, gestodene, imatinib, mifepristone, norfloxacin, norfluoxetine, voriconazole*

Based on <http://medicine.iupui.edu/clinpharm/ddis/table.asp> as of December 01, 2009

* Voriconazole (unclassified as per the Indiana University DDI table)

Strong inhibitor according to the following reference:

(<http://www.nature.com/clpt/journal/v80/n5/pdf/clpt2006438a.pdf>)

1.

Table 3-7 Clinically relevant drug interactions mediated by PgP

PgP Substrates	PgP Inhibitors in vivo	PgP Inducers
digoxin, fexofenadine, indinavir, vincristine, colchicine, topotecan, paclitaxel	amiodarone, azithromycin, captopril, carvedilol, clarithromycin, conivaptan, cyclosporine, diltiazem, elacridar, erythromycin, felodipine, (GF120918), itraconazole, ketocoanzole, lopinavir, (LY335979), mibefradil, nifedipine, nitrendipine, (PSC833), quinidine, ranolazine, ritonavir, talinolol, valsopdar, verapamil	rifampin, St John's wort

Reference:

Internal Clinical Pharmacology Drug-drug interaction (DDI) memo, updated Dec. 2, 2009, which summarizes DDI data from three sources including the FDA's "Guidance for Industry, Drug Interaction Studies, the University of Washington's Drug Interaction Database, and Indiana University School of Medicine's Drug Interaction Table."

NOTES:<http://www.fda.gov/downloads/Drugs/GuidanceComplianceRegulatoryInformation/Guidances/UCM072101.pdf>

This list of clinically relevant drug interactions is updated as of December 02, 2009

